10.3 Technical Details of Pharmacokinetic Analysis

- 
- 
- 
- 
- 
- 
- 
- 
- 
- 

10.4 Pharmacokinetic/Pharmacodynamic Analysis

11 Pharmacodynamic Analyses

The pharmacodynamic analysis set will be used for the analyses in [Section 11.3](#).

11.1 Method of Calculating Endpoints

For pharmacodynamic endpoints that require calculation, the calculation method is shown below. If the Allowable Time Windows for Postdose Examinations/Assessments specified in the protocol ([Table 1.3-2](#)) is exceeded, pharmacodynamic endpoints using values for that time cannot be calculated. However, 24-hour urine volume, water intake, fluid balance and urinary excretion of electrolytes (sodium, potassium), and urinary excretion of aquaporin 2 cannot be calculated only if the end point of the last interval exceeds the allowable time windows for postdose examinations/assessments specified in the protocol.

- 1) Urinary excretion rate (mL/h): /1-hour fluid intake/fluid balance: urine volume/fluid intake/fluid balance in each interval will be converted to excretion per unit time (1 hour).
- 2) Fluid balance: Fluid intake during urine collection interval – interval urine volume
- 3) Urinary electrolytes (sodium, potassium) and aquaporin 2 excretion: Calculated as the product of the concentration in the interval urine and the urine volume.
- 4) 24-hour urine volume/fluid intake/fluid balance and urinary electrolyte (sodium, potassium) excretion/urinary aquaporin-2 excretion: Calculate the sum of the values of urine volume/fluid intake/fluid balance/excretion in each interval from Day 1 to 0-24 hours after administration on Day 13, 0-24 and 24-48 hours after administration on Day 14, and 0-24 and 24-48 hours after the final administration in early completion subjects and discontinued subjects. If any interval is missing, the cumulative value will also be considered missing unless that interval volume is separately measured.
- 5) Free water clearance (mL/min): Calculated for each urine collection interval of 0-24 hours after administration on Day 1 and Day 7, 0-48 hours after administration on Day 14, and 0-48 hours after the final IMP administration in subjects who completed the study early and those who discontinued the study by the following formula. The values of serum osmolality used to calculate the free water clearance at each assessment time are shown in the table below. The mean values of serum osmolality (before) and serum osmolality (after) are used (if only one value is available, that value is used).
 - Free water clearance = Urine excretion rate (mL/min) \times (serum osmolality – urine osmolality) / serum osmolality

Table 11.1-1 Serum Osmolality Values Used to Calculate Free Water Clearance			
Timing (Day)	Timing (Urine Collection Interval)	Serum Osmolality (Before)	Serum Osmolality (After)
-1	0-4 hours after breakfast	Day 1 predose	—
-1	4-8 hours after breakfast	Day 1 predose	—
-1	8-12 hours after breakfast	Day 1 predose	—
-1	12-24 hours after breakfast	Day 1 predose	—
1	0-4 hours postdose	Day 1 predose	Day 1 4-6 hours postdose
1	4-8 hours postdose	4-6 hours postdose	—
1	8-12 hours postdose	Day 1 8-12 hours postdose	—
1	12-24 hours postdose	Day 1 8-12 hours postdose	Day 2 predose
7	0-4 hours postdose	Day 7 predose	Day 7 4-6 hours postdose
7	4-8 hours postdose	Day 7 4-6 hours postdose	—
7	8-12 hours postdose	Day 7 8-12 hours postdose	—
7	12-24 hours postdose	Day 7 8-12 hours postdose	Day 8 predose
14	0-4 hours postdose	Day 14 predose	EOT examination before breakfast
14	4-8 hours postdose	Day 14 predose	EOT examination before breakfast
14	8-12 hours postdose	Day 14 predose	EOT examination before breakfast
14	12-24 hours postdose	Day 14 predose	EOT examination before breakfast
14	24-28 hours postdose	EOT examination before breakfast	Post-treatment observation examination before breakfast
14	28-32 hours postdose	EOT examination before breakfast	Post-treatment observation examination before breakfast
14	32-36 hours postdose	EOT examination before breakfast	Post-treatment observation examination before breakfast
14	36-48 hours postdose	EOT examination before breakfast	Post-treatment observation examination before breakfast
Early completers/ EOT examination	Daily urine volume (EOT examination)	EOT examination before breakfast	—
Withdrawal Examination	Daily urine volume (withdrawal examination)	Withdrawal examination before breakfast	—

6) eGFRcre (mL/min/1.73m²): Calculated from serum creatinine concentration, sex, and age on Day 1, Day 8, Day 15, and the day after the last dose for early completers and withdrawals, using the CKD-EPI formula¹ and the GFR estimation formula for Japanese².

- CKD-EPI formula (males):
When serum creatine concentration ≤ 0.9 mg/dL:
$$\text{eGFR} = 141 \times (\text{serum creatinine concentration} / 0.9)^{-0.411} \times 0.993^{\text{age}}$$
When serum creatine concentration > 0.9 mg/dL:
$$\text{eGFR} = 141 \times (\text{serum creatinine concentration} / 0.9)^{-1.209} \times 0.993^{\text{age}}$$
CKD-EPI formula (females):
$$\text{eGFR} = 144 \times (\text{serum creatinine concentration} / 0.9)^{-0.329} \times 0.993^{\text{age}}$$
When serum creatine concentration > 0.9 mg/dL:
$$\text{eGFR} = 144 \times (\text{serum creatinine concentration} / 0.9)^{-1.209} \times 0.993^{\text{age}}$$
- Estimated GFR in Japanese (males):
$$\text{eGFR} = 194 \times \text{serum creatinine concentration}^{-1.094} \times \text{age}^{-0.287}$$
Estimated GFR in Japanese (females):
$$\text{eGFR} = 194 \times \text{serum creatinine concentration}^{-1.094} \times \text{age}^{-0.287} \times 0.739$$

7) eGFRcys: Calculated from serum cystatin C concentration, sex, and age on Day 1, Day 8, Day 15, and the day after the last dose for early completer and withdrawals, using the GFR estimation formula³ for Japanese.

- For males:
$$(104 \times \text{serum cystatin C concentration [mg/L]}^{-1.019} \times 0.996^{\text{age}}) - 8$$
- For females:
$$(104 \times \text{serum cystatin C concentration (mg/L)}^{-1.019} \times 0.996^{\text{age}} \times 0.929) - 8$$

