11.3 Statistical Methods

Descriptive statistics of the actual values for each pharmacodynamic endpoint at each time point and descriptive statistics of the changes from baseline at each time point will be calculated by treatment group (by dose of OPC-131461). If the allowable time windows for postdose examinations/assessments specified in the protocol is exceeded, the values for that time will not be included in the tabulation.

The descriptive statistics to be calculated will be the number of subjects tabulated, mean, standard deviation, minimum, median, and maximum.

For urinary excretion rate, 1-hour fluid intake, 1-hour fluid balance, urine osmolarity, free water clearance, serum osmolality, serum Na concentration, serum K concentration, plasma AVP concentration, plasma BNP concentration, serum NT-proBNP concentration, and serum troponin I concentration, graphs of actual values or calculated values and changes from baseline (mean \pm SD) will be prepared as line graphs representing the time course. For 24-hour urine volume, 24-hour urinary Na excretion, 24-hour urinary K excretion, 24-hour fluid intake, and 24-hour fluid balance, the actual values or calculated values and changes from baseline (mean \pm SD) will be prepared as line graphs representing the time course. For 24-hour urinary aquaporin-2, a bar graph comparing calculated values and changes from baseline (mean \pm SD) will be prepared.

12 Pharmacogenomic Analyses

Not performed.

13 Exploratory Endpoint Analyses

13.1

[REDACTED]

[REDACTED]

[REDACTED]

13.2

[REDACTED]

[REDACTED]

[REDACTED]

14 Interim Analysis

[REDACTED]

15 Changes in the Planned Analyses

Table 15-1 Changes in the Planned Analyses		
Description in the Protocol	Description in the Statistical Analysis Plan	Reason for Change
9.4.3.3 Pharmacodynamic Analysis Cumulative urine volume/fluid intake/fluid balance and cumulative urine electrolyte (sodium, potassium) excretions: Sum up the values in time points for urine accumulation or fluid intake. If there are missing data in any of the intervals, the cumulative value will also be handled as missing data.	11.1 Method of Calculating Endpoints (No description)	Calculation of these pharmacodynamic endpoints was considered unnecessary.

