9.4.3.2 Pharmacokinetic Analysis For any parameter for which the number of tabulated subjects is half of the number of subjects in the analysis set or less, descriptive statistics will not be calculated.	10.2 Statistical Methods (No description)	Application of such statistical analysis methods to this analysis was considered unnecessary.

16 References

Not applicable.

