PDT-17 Descriptive Statistics for Free Water Clearance (Pharmacodynamic Analysis Set)

PDT-18 Descriptive Statistics for Serum Osmolality (Pharmacodynamic Analysis Set)

PDT-19 Descriptive Statistics for Serum Sodium Concentration (Pharmacodynamic Analysis Set)

PDT-20 Descriptive Statistics for Serum Potassium Concentration (Pharmacodynamic Analysis Set)

PDT-21 Descriptive Statistics for Serum Cystatin C Concentration (Pharmacodynamic Analysis Set)

PDT-22 Descriptive Statistics for Serum Creatinine Concentration (Pharmacodynamic Analysis Set)

PDT-23 Descriptive Statistics for Plasma AVP Concentration (Pharmacodynamic Analysis Set)

PDT-24 Descriptive Statistics for Plasma Renin Activity (Pharmacodynamic Analysis Set)

PDT-25	Descriptive Statistics for Plasma Aldosterone Concentration (Pharmacodynamic Analysis Set)
PDT-26	Descriptive Statistics for Plasma BNP Concentration (Pharmacodynamic Analysis Set)
PDT-27	Descriptive Statistics for Serum NT-pro BNP Concentration (Pharmacodynamic Analysis Set)
PDT-28	Descriptive Statistics for Serum Troponin I Concentration (Pharmacodynamic Analysis Set)
PDT-29	Descriptive Statistics for eGFRcre calculated by CKD-EPI Equation (Pharmacodynamic Analysis Set)
PDT-30	Descriptive Statistics for eGFRcre calculated by Japanese Equation (Pharmacodynamic Analysis Set)
PDT-31	Descriptive Statistics for eGFRcys calculated by Japanese Equation (Pharmacodynamic Analysis Set)
PDF-1	Mean (SD) 24-Hour Urine Volume
PDF-2	Mean (SD) Change from Baseline of 24-Hour Urine Volume
PDF-3	Mean (SD) Urine Excretion Rate on Day 1, 7, and 14
PDF-4	Mean (SD) Change from Baseline of Urine Excretion Rate on Day 1, 7, and 14
PDF-5	Mean (SD) Urine Osmolality on Day 1, 7, and 14
PDF-6	Mean (SD) Change from Baseline of Urine Osmolality on Day 1, 7, and 14
PDF-7	Mean (SD) 24-Hour Urine Excretion of Sodium
PDF-8	Mean (SD) Change from Baseline of 24-Hour Urine Excretion of Sodium
PDF-9	Mean (SD) 24-Hour Urine Excretion of Potassium
PDF-10	Mean (SD) Change from Baseline of 24-Hour Urine Excretion of Potassium
PDF-11	Mean (SD) 24-Hour Urine Excretion of Aquaporin2

PDF-12	Mean (SD) Change from Baseline of 24-Hour Urine Excretion of Aquaporin2
PDF-13	Mean (SD) 24-Hour Fluid Intake Volume
PDF-14	Mean (SD) Change from Baseline of 24-Hour Fluid Intake Volume
PDF-15	Mean (SD) Hourly Fluid Intake Volume on Day 1, 7, and 14
PDF-16	Mean (SD) Change from Baseline of Hourly Fluid Intake Volume on Day 1, 7, and 14
PDF-17	Mean (SD) 24-Hour Fluid Balance

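### SAP Section 11.1: the female CKD-EPI lines carry the male creatinine divisor 0.9, so the expected downward adjustment for women vanishes and, above about 0.70 mg/dL, reverses

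*SAP*

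**What the plan says.** Section 11.1, item 6, defines eGFRcre by two equations, CKD-EPI and a Japanese equation.

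- **CKD-EPI, men:** coefficient 141, with "serum creatinine concentration} / 0.9)^{-0.411" at or below 0.9 mg/dL and exponent -1.209 above it.
- **CKD-EPI, women:** coefficient 144, with "serum creatinine concentration} / 0.9)^{-0.329" in the first line. The second line is introduced by "When serum creatine concentration > 0.9 mg/dL" and uses "serum creatinine concentration} / 0.9)^{-1.209". The same cut-off and the same upper-branch term are printed for men.
- **Japanese creatinine equation:** the line headed "Estimated GFR in Japanese (females") is the male equation multiplied by 0.739.
- **Japanese cystatin C equation (item 7):** the female term is multiplied by 0.929 before 8 is subtracted.

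The three equations carry superscripts 1 to 3, but the section "16 References" states that none apply. Section 11.3 plans "Descriptive statistics of the actual values for each pharmacodynamic endpoint at each time point", together with changes from baseline. Appendix 1 lists table PDT-29, "Descriptive Statistics for eGFRcre calculated by CKD-EPI Equation (Pharmacodynamic Analysis Set"), and Appendix 2 lists the individual values in PDATA-17.

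**The concern.** CKD-EPI as printed has a different coefficient and a different lower exponent for women, but the same divisor and the same cut-off as for men. Above 0.9 mg/dL nothing but the coefficient separates the sexes, and it moves women slightly up. The SAP's other two eGFR equations both move women down. One of those two uses the same serum creatinine value as CKD-EPI and estimates the same quantity.

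If the lines are programmed as they stand, every woman's CKD-EPI value in PDT-29 and PDATA-17 is affected, and so is her absolute change from baseline. Arm means would also move with the proportion of women in each arm, which can differ by chance with 31 subjects per group. With no reference list, the programmer cannot trace the source from this document and would code what is printed.

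**Working it through.** The SAP states no result to reproduce, so the check evaluates the printed equations directly. Let *s* be serum creatinine in mg/dL. At equal age the term 0.993^age cancels.

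**Inputs (Section 11.1, items 6 and 7).** Men: coefficient 141, divisor 0.9, exponents -0.411 and -1.209. Women: coefficient 144, divisor 0.9, exponents -0.329 and -1.209. Female factors in the Japanese equations: 0.739 (creatinine) and 0.929 (cystatin C).

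**1. Female/male ratio as printed**

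- Above 0.9: 144/141 = 1.021.
- At or below 0.9: (144/141) × (s/0.9)^(0.411 − 0.329) = 1.0213 × (s/0.9)^0.082.
- The ratio equals 1 at s = 0.9 × (141/144)^(1/0.082) = 0.696 mg/dL.

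| s (mg/dL) | 0.6 | 0.70 | 0.8 | above 0.9 |
|---|---|---|---|---|
| Female/male | 0.988 | 1.000 | 1.012 | 1.021 |

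**2. Comparison with the SAP's other equations, age 75**

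| Equation | Marker | Man | Woman | Female/male |
|---|---|---|---|---|
| CKD-EPI as printed | creatinine 1.5 mg/dL | 44.9 | 45.9 | 1.021 |
| Japanese creatinine | creatinine 1.5 mg/dL | 36.1 | 26.6 | 0.739 |
| Japanese cystatin C | cystatin C 1.5 mg/L | 42.9 | 39.3 | 0.916 |

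From one creatinine value, the two creatinine equations differ by 24% in men (44.9/36.1 = 1.24) but by about 72% in women (45.9/26.6 = 1.72). Everywhere above 0.9 mg/dL, the CKD-EPI/Japanese ratio is 1.021/0.739 = 1.38 times as large in women as in men.

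**3. What divisor would restore the direction**

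With a female divisor *k*, the ratio above 0.9 mg/dL is (144/141) × (k/0.9)^1.209. It falls below 1 when k < 0.9 × (141/144)^(1/1.209) = 0.884. A match to the SAP's own factor of 0.739 would need k = 0.9 × (0.739 × 141/144)^(1/1.209) = 0.689. The two equations need not agree, so this only gives the scale.

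**4. Size of the overstatement**

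The SAP does not give the correct *k*; 0.70 to 0.85 is an assumption. Printed female values exceed the corrected ones by the factor (0.9/k)^1.209 above 0.9 mg/dL, and by (0.9/k)^0.329 at or below 0.7 mg/dL.

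| Assumed k | 0.70 | 0.75 | 0.80 | 0.85 |
|---|---|---|---|---|
| Overstatement above 0.9 mg/dL | 35.5% | 24.7% | 15.3% | 7.2% |
| Overstatement at or below 0.7 mg/dL | 8.6% | 6.2% | 4.0% | 1.9% |

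**5. Example.** For a woman aged 75 with creatinine 1.0 mg/dL, the printed formula gives 144 × (1.0/0.9)^(−1.209) × 0.993^75 = 74.9 mL/min/1.73 m². The corrected value would be 55.2 (k = 0.70) to 69.9 (k = 0.85). A man of the same age and creatinine scores 73.3. If her creatinine rises to 1.2 mg/dL, her change is −14.8 as printed, against −10.9 to −13.8.

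**The case against.** The printed female formula is not self-contradictory. Divisor and cut-off are both 0.9, so its two branches join at 144 × 0.993^age, and no figure stated in the SAP is violated. The argument rests on direction alone. The Japanese equations are separate, one uses a different marker, and nothing in the SAP requires all three to agree. Only the 2.1% excess follows from the document; the 7% to 36% range depends on an assumed constant. A lower bound of 0.60, for example, would give 63% above 0.9 mg/dL. The condition for the first female line is not visible in the available text, so the PDF conversion may have damaged this block. The output is descriptive, percent change above the cut-off is unaffected by a constant factor, and serum creatinine, Japanese eGFRcre and eGFRcys have their own tables.

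Some of this stands. The size is conditional on the assumption, the impact is limited, and the missing condition is not counted here as an error. The main point remains. A sex adjustment that almost disappears and changes sign in one of two equations applied to the same sample is strong evidence of a copied constant. The value 0.9 occurs three times in the female block, so a single misread digit is unlikely. Section 11.3 tabulates absolute values and absolute changes, so the invariance of percent change does not protect PDT-29.

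**Conclusion.** The concern holds. As printed, the CKD-EPI equation gives women a higher eGFR than men of the same age and creatinine from about 0.70 mg/dL upward (2.1% higher above 0.9), opposite to both other eGFR equations in the SAP. That much needs no outside figure. The error in female values depends on the true constant: 7.2% to 35.5% above 0.9 mg/dL if it lies between 0.85 and 0.70. The SAP expects values in that upper branch, since Table 8.4-1 includes a creatinine subgroup split at 2 mg/dL.

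The damage is confined to PDT-29 and PDATA-17, which report a secondary pharmacodynamic endpoint descriptively. The primary endpoint, sample size, dose-response contrasts, serum creatinine (PDT-22), Japanese eGFRcre (PDT-30) and eGFRcys (PDT-31) are unaffected. It should be corrected before programming, but it does not threaten the trial's main conclusions.

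**What to change.** - Take the female divisor and cut-off from the CKD-EPI source cited as reference 1.
- Correct both female lines and the female upper cut-off, and state the matching lower-branch condition for women.
- Replace the empty Section 16 with references 1 to 3, so that all three equations can be verified against their sources.

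The cost is two formula lines, one cut-off and three reference entries. No new data are needed. If values have already been derived, they can be recalculated from stored creatinine, age and sex.

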11.2 Definition of Baseline

For urine volume, urine excretion rate, urine osmolarity, urine Na excretion, urine K excretion, urine aquaporin-2 excretion, fluid intake, fluid balance, and free water clearance, the values on Day -1 corresponding to each measurement interval in the treatment period will be used.

eGFR is defined as the predose value on Day 1.

Blood endpoints (serum osmolality, serum Na concentration, serum K concentration, serum cystatin C concentration, serum creatinine concentration, plasma A VP concentration, plasma renin activity, plasma aldosterone concentration, plasma BNP concentration, serum NT-pro BNP concentration, and serum troponin I concentration) are used for pharmacodynamic evaluation before IMP administration on Day 1.

The significant figures of each baseline value shall be consistent with those of each endpoint.

11.3 Statistical Methods

Descriptive statistics of the actual values for each pharmacodynamic endpoint at each time point and descriptive statistics of the changes from baseline at each time point will be calculated by treatment group (by dose of OPC-131461). If the allowable time windows for postdose examinations/assessments specified in the protocol is exceeded, the values for that time will not be included in the tabulation.

The descriptive statistics to be calculated will be the number of subjects tabulated, mean, standard deviation, minimum, median, and maximum.

For urinary excretion rate, 1-hour fluid intake, 1-hour fluid balance, urine osmolarity, free water clearance, serum osmolality, serum Na concentration, serum K concentration, plasma AVP concentration, plasma BNP concentration, serum NT-proBNP concentration, and serum troponin I concentration, graphs of actual values or calculated values and changes from baseline (mean \pm SD) will be prepared as line graphs representing the time course. For 24-hour urine volume, 24-hour urinary Na excretion, 24-hour urinary K excretion, 24-hour fluid intake, and 24-hour fluid balance, the actual values or calculated values and changes from baseline (mean \pm SD) will be prepared as line graphs representing the time course. For 24-hour urinary aquaporin-2, a bar graph comparing calculated values and changes from baseline (mean \pm SD) will be prepared.

12 Pharmacogenomic Analyses

Not performed.

13 Exploratory Endpoint Analyses

13.1

[REDACTED]

[REDACTED]

[REDACTED]

13.2

[REDACTED]

[REDACTED]

[REDACTED]

14 Interim Analysis

[REDACTED]

15 Changes in the Planned Analyses

Table 15-1 Changes in the Planned Analyses		
Description in the Protocol	Description in the Statistical Analysis Plan	Reason for Change
9.4.3.3 Pharmacodynamic Analysis Cumulative urine volume/fluid intake/fluid balance and cumulative urine electrolyte (sodium, potassium) excretions: Sum up the values in time points for urine accumulation or fluid intake. If there are missing data in any of the intervals, the cumulative value will also be handled as missing data.	11.1 Method of Calculating Endpoints (No description)	Calculation of these pharmacodynamic endpoints was considered unnecessary.
9.4.3.2 Pharmacokinetic Analysis For any parameter for which the number of tabulated subjects is half of the number of subjects in the analysis set or less, descriptive statistics will not be calculated.	10.2 Statistical Methods (No description)	Application of such statistical analysis methods to this analysis was considered unnecessary.

16 References

Not applicable.

Appendix 1 List of Summary Tables

CT-1.1 Subject Disposition (Screened Subjects)

CT-1.2 Analysis Set (Randomized Subjects)

CT-2.1 Reasons for Discontinuation (Randomized Subjects)

CT-2.2 Protocol Deviations (Randomized Subjects)

CT-3.1.1 Demographic and Baseline Characteristics (Full Analysis Set)

CT-3.1.2 Demographic and Baseline Characteristics (Safety Analysis Set)

CT-3.2.1 Underlying Disease Leading to Heart Failure (Full Analysis Set)

CT-3.2.2 Underlying Disease Leading to Heart Failure (Safety Analysis Set)

CT-3.2.3 Medical History (Full Analysis Set)

CT-3.2.4 Medical History (Safety Analysis Set)

CT-3.3.1 Baseline Disease Evaluation (Full Analysis Set)

CT-3.3.2 Baseline Disease Evaluation (Safety Analysis Set)

CT-4.1 Concomitant Medications and Therapy Used on the First Day of Investigational Medicinal Product (Full Analysis Set)

CT-4.2 Concomitant Medications and Therapy Used on the First Day of Investigational Medicinal Product (Safety Analysis Set)

CT-5.1 Analysis of Covariance for Change from Baseline in Body Weight to Last Assessment Time Point (the Day After Investigational Medicinal Product Administration) by Day 8 (Full Analysis Set)

CT-5.2 Analysis of Dose Response for Change from Baseline in Body Weight to Last Assessment Time Point (the Day After Investigational Medicinal Product Administration) by Day 8 (Full Analysis Set)

CT-5.3 Analysis of Covariance for Change from Baseline in Body Weight to Last Assessment Time Point (the Day After Investigational Medicinal Product Administration) by Day 15 (Full Analysis Set)

CT-5.4 Analysis of Dose Response for Change from Baseline in Body Weight to Last Assessment Time Point (the Day After Investigational Medicinal Product Administration) by Day 15 (Full Analysis Set)

CT-5.5 Descriptive Statistics for Change from Baseline in Body Weight by Visit (Full Analysis Set)

CT-5.6 Descriptive Statistics for Change Rate from Baseline in Body Weight by Visit (Full Analysis Set)

CT-5.7.1 Subgroup Analysis of Analysis of Covariance for Change from Baseline in Body Weight to Last Assessment Time Point (the Day After Investigational Medicinal Product Administration) by Day 8 (Full Analysis Set)

CT-5.7.2 Subgroup Analysis for Change from Baseline in Body Weight to Last Assessment Time Point (the Day After Investigational Medicinal Product Administration) by Day 8 (Full Analysis Set)

CT-6.1.1 Improvement Rate for Lower Limb Edema and Pulmonary Congestion (Full Analysis Set)

CT-6.1.2 Improvement Rate for Lower Limb Edema and Pulmonary Congestion by Visit (Full Analysis Set)

CT-6.1.3 Resolution Rate for Lower Limb Edema and Pulmonary Congestion (Full Analysis Set)

CT-6.1.4 Time to Resolution for Lower Limb Edema and Pulmonary Congestion (Full Analysis Set)

CT-6.1.5 Shift Table for Lower Limb Edema and Pulmonary Congestion by Visit (Full Analysis Set)

CT-6.1.6 Time to Improvement for Lower Limb Edema and Pulmonary Congestion (Full Analysis Set)

CT-6.2.1 Resolution Rate for Pulmonary rales and Third Cardiac Sound (Full Analysis Set)

CT-6.2.2 Time to Resolution for Pulmonary rales and Third Cardiac Sound (Full Analysis Set)

CT-6.2.3 Shift Table for Pulmonary rales and Third Cardiac Sound by Visit (Full Analysis Set)

CT-6.3.1 Analysis of Covariance for Change from Baseline in Jugular Venous Distension, Hepatomegaly and Cardiothoracic Ratio (Full Analysis Set)

- CT-6.3.2 Descriptive Statistics for Jugular Venous Distension, Hepatomegaly and Cardiothoracic Ratio by Visit (Full Analysis Set)
- CT-6.3.3 Shift Table of Presence or Absence for Jugular Venous Distension and Hepatomegaly by Visit (Full Analysis Set)
- CT-6.3.4 Time to Resolution for Jugular Venous Distension and Hepatomegaly (Full Analysis Set)
- CT-6.4.1 Improvement Rate for NYHA Classification (Full Analysis Set)
- CT-6.4.2 Shift Table for NYHA Classification by Visit (Full Analysis Set)
- CT-7.1 Extent of Exposure to Investigational Medicinal Product (Safety Analysis Set)
- CT-7.2 Treatment Compliance (Full Analysis Set)
- CT-8.1 Overall Summary of Adverse Events (Safety Analysis Set)
- CT-8.2 Incidence of Treatment-emergent Adverse Events by MedDRA System Organ Class and Preferred Term (Safety Analysis Set)
- CT-8.3 Incidence of Drug-related Treatment-emergent Adverse Events by MedDRA System Organ Class and Preferred Term (Safety Analysis Set)
- CT-8.4 Incidence of Treatment-emergent Adverse Events by Severity by MedDRA System Organ Class and Preferred Term (Safety Analysis Set)
- CT-8.5 Incidence of Drug-related Treatment-emergent Adverse Events by Severity by MedDRA System Organ Class and Preferred Term (Safety Analysis Set)
- CT-8.6 Incidence of Treatment-emergent Adverse Events Occurring in 5% or More of Subjects in Any Treatment Group by MedDRA System Organ Class and Preferred Term (Safety Analysis Set)
- CT-8.7 Incidence of Drug-related Treatment-emergent Adverse Events Occurring in 5% or More of Subjects in Any Treatment Group by MedDRA System Organ Class and Preferred Term (Safety Analysis Set)
- CT-8.8.1 Incidence of Treatment-emergent Adverse Events by MedDRA System Organ Class, Preferred Term and Period of First Onset in Category 1 (Safety Analysis Set)

CT-8.8.2 Incidence of Drug-related Treatment-emergent Adverse Events by MedDRA System Organ Class, Preferred Term and Period of First Onset in Category 1 (Safety Analysis Set)

CT-8.9.1 Incidence of Treatment-emergent Adverse Events by MedDRA System Organ Class, Preferred Term and Period of First Onset in Category 2 (Safety Analysis Set)

CT-8.9.2 Incidence of Drug-related Treatment-emergent Adverse Events by MedDRA System Organ Class, Preferred Term and Period of First Onset in Category 2 (Safety Analysis Set)

CT-8.10 Incidence of Treatment-emergent Adverse Events with an outcome of death by MedDRA System Organ Class and Preferred Term (Safety Analysis Set)

CT-8.11 Incidence of Drug-related Treatment-emergent Adverse Events with an outcome of death by MedDRA System Organ Class and Preferred Term (Safety Analysis Set)

CT-8.12 Incidence of Serious Treatment-emergent Adverse Events by MedDRA System Organ Class and Preferred Term (Safety Analysis Set)

CT-8.13 Incidence of Drug-related Serious Treatment-emergent Adverse Events by MedDRA System Organ Class and Preferred Term (Safety Analysis Set)

CT-8.14 Incidence of Treatment-emergent Adverse Events Leading to Discontinuation of Investigational Medicinal Product Administration by MedDRA System Organ Class and Preferred Term (Safety Analysis Set)

CT-8.15 Incidence of Drug-related Treatment-emergent Adverse Events Leading to Discontinuation of Investigational Medicinal Product Administration by MedDRA System Organ Class and Preferred Term (Safety Analysis Set)

CT-9.1 Listing of Deaths (Randomized Subjects)

CT-9.2 Listing of Serious Adverse Events Other Than Death (Randomized Subjects)

CT-9.3 Listing of Adverse Events Leading to Discontinuation of Investigational Medicinal Product Administration (Randomized Subjects)

CT-10.1.1 Mean Change from Baseline in Clinical Laboratory Test Results (Biochemistry) (Safety Analysis Set)

- CT-10.1.2 Mean Change from Baseline in Clinical Laboratory Test Results (Hematology and Coagulation) (Safety Analysis Set)
- CT-10.1.3 Mean Change from Baseline in Clinical Laboratory Test Results (Urinalysis) (Safety Analysis Set)
- CT-10.2 Shift Tables of Clinical Laboratory Test Results (Qualitative Urinalysis) (Safety Analysis Set)
- CT-10.3.1 Shift Tables of Clinical Laboratory Test Results (Biochemistry) (Safety Analysis Set)
- CT-10.3.2 Shift Tables of Clinical Laboratory Test Results (NA, K) (Safety Analysis Set)
- CT-10.3.3 Shift Tables of Clinical Laboratory Test Results (Hematology and Coagulation) (Safety Analysis Set)
- CT-10.3.4 Shift Tables of Clinical Laboratory Test Results (Urinalysis) (Safety Analysis Set)
- CT-10.4.1 Listing of Abnormal Laboratory Findings (Randomized Subjects)
- CT-10.4.2 Listing of Potential Drug-Induced Liver Injury (Randomized Subjects)
- CT-10.5 Incidence of Potential Drug-Induced Liver Injury (Safety Analysis Set)
- CT-11.1 Mean Change from Baseline in Vital Signs (Safety Analysis Set)
- CT-11.2 Incidence of Systolic Blood Pressure Less Than 90 mmHg (Safety Analysis Set)
- CT-12.1 Mean Change from Baseline in Electrocardiogram Results (Safety Analysis Set)
- CT-12.2 Shift Table of 12-Lead ECG Findings (Normal/Abnormal Assessments) (Safety Analysis Set)
- CT-12.3 Incidence of Categorical Changes in Electrocardiogram Results (Safety Analysis Set)
- CT-13.1 [REDACTED]
- CT-13.2.1 [REDACTED]
- CT-13.2.2 [REDACTED]

CF-1.1 Bar Graph for Change From Baseline in Body Weight to Last Assessment Time Point (the Day After Investigational Medicinal Product Administration) by Day 8 (Full Analysis Set)

CF-1.2 Bar Graph for Change From Baseline in Body Weight to Last Assessment Time Point (the Day After Investigational Medicinal Product Administration) by Day 15 (Full Analysis Set)

CF-2 Kaplan Meier Curve of Time to Improvement for Lower Limb Edema and Pulmonary Congestion (Full Analysis Set)

CF-3 Kaplan Meier Curve of Time to Resolution for Lower Limb Edema and Pulmonary Congestion (Full Analysis Set)

CF-4 Kaplan Meier Curve of Time to Resolution for Pulmonary rales and Third Cardiac Sound (Full Analysis Set)

CF-5 Kaplan Meier Curve of Time to Resolution for Jugular Venous Distension and Hepatomegaly (Full Analysis Set)

CF-6 Scatter Plot for Clinical Laboratory Tests

PKT-1.1 Individual and Summary of OPC-131461 Plasma Concentration Following Single Oral Administration of OPC-131461 (Pharmacokinetics Analysis Set)

PKT-1.2 Individual and Summary of M35101 Plasma Concentration Following Single Oral Administration of OPC-131461 (Pharmacokinetics Analysis Set)

PKT-1.3 Individual and Summary of M35103 Plasma Concentration Following Single Oral Administration of OPC-131461 (Pharmacokinetics Analysis Set)

PKT-2.1 Individual and Summary of OPC-131461 Plasma Pharmacokinetic Parameters Following Single Oral Administration of OPC-131461 (Pharmacokinetics Analysis Set)

PKT-2.2 Individual and Summary of M35101 Plasma Pharmacokinetic Parameters Following Single Oral Administration of OPC-131461 (Pharmacokinetics Analysis Set)

PKT-2.3 Individual and Summary of M35103 Plasma Pharmacokinetic Parameters Following Single Oral Administration of OPC-131461 (Pharmacokinetics Analysis Set)

PKT-3.1 Individual and Summary of OPC-131461 Plasma Concentration Following Multiple Oral Administration of OPC-131461 (Day 7) (Pharmacokinetics Analysis Set)

PKT-3.2 Individual and Summary of M35101 Plasma Concentration Following Multiple Oral Administration of OPC-131461 (Day 7) (Pharmacokinetics Analysis Set)

PKT-3.3 Individual and Summary of M35103 Plasma Concentration Following Multiple Oral Administration of OPC-131461 (Day 7) (Pharmacokinetics Analysis Set)

PKT-4.1 Individual and Summary of OPC-131461 Plasma Concentration Following Multiple Oral Administration of OPC-131461 (Day 14) (Pharmacokinetics Analysis Set)

PKT-4.2 Individual and Summary of M35101 Plasma Concentration Following Multiple Oral Administration of OPC-131461 (Day 14) (Pharmacokinetics Analysis Set)

PKT-4.3 Individual and Summary of M35103 Plasma Concentration Following Multiple Oral Administration of OPC-131461 (Day 14) (Pharmacokinetics Analysis Set)

PKT-5.1 Individual and Summary of OPC-131461 Plasma Trough Concentration Following Oral Administration of OPC-131461 (Pharmacokinetics Analysis Set)

PKT-5.2 Individual and Summary of M35101 Plasma Trough Concentration Following Oral Administration of OPC-131461 (Pharmacokinetics Analysis Set)

PKT-5.3 Individual and Summary of M35103 Plasma Trough Concentration Following Oral Administration of OPC-131461 (Pharmacokinetics Analysis Set)

PKT-6.1 Individual and Summary of OPC-131461 Plasma Pharmacokinetic Parameters Following Multiple Oral Administration of OPC-131461 (Day 7) (Pharmacokinetics Analysis Set)

PKT-6.2 Individual and Summary of M35101 Plasma Pharmacokinetic Parameters Following Multiple Oral Administration of OPC-131461 (Day 7) (Pharmacokinetics Analysis Set)

PKT-6.3 Individual and Summary of M35103 Plasma Pharmacokinetic Parameters Following Multiple Oral Administration of OPC-131461 (Day 7) (Pharmacokinetics Analysis Set)

PKT-7.1 Individual and Summary of OPC-131461 Plasma Pharmacokinetic Parameters Following Multiple Oral Administration of OPC-131461 (Day 14) (Pharmacokinetics Analysis Set)

PKT-7.2 Individual and Summary of M35101 Plasma Pharmacokinetic Parameters Following Multiple Oral Administration of OPC-131461 (Day 14) (Pharmacokinetics Analysis Set)

PKT-7.3 Individual and Summary of M35103 Plasma Pharmacokinetic Parameters Following Multiple Oral Administration of OPC-131461 (Day 14) (Pharmacokinetics Analysis Set)

PKT-8.1 Individual and Summary of OPC-131461 Plasma Accumulation Parameters Following Multiple Oral Administration of OPC-131461 (Pharmacokinetics Analysis Set)

PKT-8.2 Individual and Summary of M35101 Plasma Accumulation Parameters Following Multiple Oral Administration of OPC-131461 (Pharmacokinetics Analysis Set)

PKT-8.3 Individual and Summary of M35103 Plasma Accumulation Parameters Following Multiple Oral Administration of OPC-131461 (Pharmacokinetics Analysis Set)

PKT-9 Dose Proportionality of OPC-131461 Pharmacokinetic Parameters (Pharmacokinetics Analysis Set)

PKF-1.1 Mean OPC-131461 Plasma Concentrations Following Single Oral Administration of OPC-131461 (Pharmacokinetics Analysis Set)

PKF-1.2 Mean M35101 Plasma Concentrations Following Single Oral Administration of OPC-131461 (Pharmacokinetics Analysis Set)

PKF-1.3 Mean M35103 Plasma Concentrations Following Single Oral Administration of OPC-131461 (Pharmacokinetics Analysis Set)

PKF-2.1 Median OPC-131461 Plasma Concentrations Following Single Oral Administration of OPC-131461 (Pharmacokinetics Analysis Set)

PKF-2.2 Median M35101 Plasma Concentrations Following Single Oral Administration of OPC-131461 (Pharmacokinetics Analysis Set)

PKF-2.3 Median M35103 Plasma Concentrations Following Single Oral Administration of OPC-131461 (Pharmacokinetics Analysis Set)

PKF-3.1 Individual OPC-131461 Plasma Concentrations Following Single Oral Administration of OPC-131461 (Pharmacokinetics Analysis Set)

PKF-3.2 Individual M35101 Plasma Concentrations Following Single Oral Administration of OPC-131461 (Pharmacokinetics Analysis Set)

PKF-3.3 Individual M35103 Plasma Concentrations Following Single Oral Administration of OPC-131461 (Pharmacokinetics Analysis Set)

PKF-4.1 Mean OPC-131461 Plasma Concentrations Following Multiple Oral Administration of OPC-131461 on Day 7 (Pharmacokinetics Analysis Set)

PKF-4.2 Mean M35101 Plasma Concentrations Following Multiple Oral Administration of OPC-131461 on Day 7 (Pharmacokinetics Analysis Set)

PKF-4.3 Mean M35103 Plasma Concentrations Following Multiple Oral Administration of OPC-131461 on Day 7 (Pharmacokinetics Analysis Set)

PKF-5.1 Median OPC-131461 Plasma Concentrations Following Multiple Oral Administration of OPC-131461 on Day 7 (Pharmacokinetics Analysis Set)

PKF-5.2 Median M35101 Plasma Concentrations Following Multiple Oral Administration of OPC-131461 on Day 7 (Pharmacokinetics Analysis Set)

PKF-5.3 Median M35103 Plasma Concentrations Following Multiple Oral Administration of OPC-131461 on Day 7 (Pharmacokinetics Analysis Set)

PKF-6.1 Mean OPC-131461 Plasma Concentrations Following Multiple Oral Administration of OPC-131461 on Day 14 (Pharmacokinetics Analysis Set)

PKF-6.2 Mean M35101 Plasma Concentrations Following Multiple Oral Administration of OPC-131461 on Day 14 (Pharmacokinetics Analysis Set)

PKF-6.3 Mean M35103 Plasma Concentrations Following Multiple Oral Administration of OPC-131461 on Day 14 (Pharmacokinetics Analysis Set)

PKF-7.1 Median OPC-131461 Plasma Concentrations Following Multiple Oral Administration of OPC-131461 on Day 14 (Pharmacokinetics Analysis Set)

PKF-7.2 Median M35101 Plasma Concentrations Following Multiple Oral Administration of OPC-131461 on Day 14 (Pharmacokinetics Analysis Set)

PKF-7.3 Median M35103 Plasma Concentrations Following Multiple Oral Administration of OPC-131461 on Day 14 (Pharmacokinetics Analysis Set)

PKF-8.1 Mean OPC-131461 Plasma Trough Concentrations Following Oral Administration of OPC-131461 (Pharmacokinetics Analysis Set)

PKF-8.2 Mean M35101 Plasma Trough Concentrations Following Oral Administration of OPC-131461 (Pharmacokinetics Analysis Set)

PKF-8.3 Mean M35103 Plasma Trough Concentrations Following Oral Administration of OPC-131461 (Pharmacokinetics Analysis Set)

PKF-9.1 Median OPC-131461 Plasma Trough Concentrations Following Oral Administration of OPC-131461 (Pharmacokinetics Analysis Set)

PKF-9.2 Median M35101 Plasma Trough Concentrations Following Oral Administration of OPC-131461 (Pharmacokinetics Analysis Set)

